Though there no adverse risk responses were reported in published

randomized controlled trials in clinical populations in the literature, there are some expected transient perceptual type responses, e.g. dizziness, limb numbness, perceived exertion, delayed onset muscle soreness. There are no significant risks of complications if BFR-RE is prescribed by certified trainers who have knowledge of appropriate protocols and contraindications to the use of occlusive stimuli. (Brandner, 2018)

The effect on muscle strength in COPDAE inpatients, which is not well studied in the literature, will be the primary outcome of this study. The effect on mobility functions, systemic muscle strength reflected by hand grip strength, health related quality of life and unplanned readmission rate within 1 month of discharge for COPDAE will be evaluated as secondary outcomes. Since BFR-RE is newly introduced to Haven of Hope Hospital and not widely used in Hospital Authority, acceptability and feasibility of this training will be explored as secondary outcomes.

Subjects

Patients with COPD acute exacerbation (COPDAE) will be recruited to find out the effect of blood flow restriction resistance exercise (BFR-RE). There will be a control group without BFR-RE for comparison. Principal investigator will screen the medical fitness of the subjects before recruiting to the study.

Inclusion criteria

1. COPD acute exacerbation (COPDAE) as the primary diagnosis for hospitalization or transfer to pulmonary wards of the Haven of Hope Hospital
2. Able to walk under supervision
3. Understand instruction in Cantonese and can give informed consent.

Exclusive criteria (Hick, 2013)

Subjects will be excluded if they have any of the following conditions:

1. Concomitant acute cardiac event	7. History of lymphectomies
2. Severe hypertension (BP > 180/100)	8. Extremities with dialysis access
	9. Vascular grafting

3. History of venous thromboembolism
4. History of peripheral vascular disease
5. Absence of posterior tibial or dorsalis pedal pulse
6. History of revascularization of the extremity
10. Current extremity infection
11. Active malignancy*
12. Open fracture / soft tissue injuries
13. Amputation to the lower extremity
14. Expected hospitalization less than 2 weeks on admission
15. Medications known to increase clotting risks
16. Isolation / Contact precaution requirement (e.g. MRSA status, CD toxin +ve status, etc.)

*Active malignancy (Kearon,2016) is defined as follow:

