- The 3rd generation tourniquet system features a built-in LOP measurement capability. This allows a personalized tourniquet pressure for each individual patient and eliminated the need to account for cuff width, limb size or blood pressure.

Determination of Leg dominance (Melick, 2017)

Since mobility is a bilateral mobilizing task, the leg dominance will be defined by the participant's preferred leg to shoot a ball when being asked the following question: "If you would shoot a ball on a target, which leg would you use to shoot the ball?"

Determination of completeness of training

80% of the whole course of in-patient additional muscle strength training (i.e. 10 out of 12 sessions)

Determination of acceptance of program

5-point Likert scale will be given to participants after the additional muscle strength training (i.e. very like, like, no comment, dislike, very dislike)

Data collection timepoint

- Baseline
- After completeness of training (i.e. at least 10 sessions of training)

Clinical investigations

- Laboratory tests at baseline and post training program
 - ✧ Clotting profile, Complete blood count (CBC), liver function test (LFT), renal function test (RFT), serum creatinine kinase level (CK), serum lactic acid level, C-reactive protein (CRP)
 - ✧ Estimated 32ml of venous blood in total will be needed for both pre and post training blood tests.
 - ✧ Myoglobin in urine
- Spirometry before discharge of current admission

Primary outcome:

Localized Muscle Strength (Robles, 2011; Hul ,2004)

- Muscle strength is operationally defined as subject's capability for the exertion of force or torque to an external dynamometer over a specified period of time. (Kroemer, 1980)
- Maximal voluntary isometric contraction (MVIC) of knee extension of the dominant leg, with a unit Newton (N), will be assessed by computer dynamometry.

Secondary outcomes:

- **Functional test**
 - ✧ Short physical performance battery (SPPB) (Mora, 2015)
Gait speed with 4m distance, Balance test & repeated chair stands test
 - ✧ 6-minute walk test (Holland, 2010)
- **Systemic muscle strength** (Jeong, 2017; Yu, 2017)
 - ✧ Hand grip strength, a non-invasive marker of systemic skeletal muscle strength and function, is assessed by handheld grip dynamometer of dominant hand
- **Health related quality of life**
 - ✧ Self-administered Chinese version of COPD assessment test (CAT) (Karlah,2016)
- **Acceptability of BFR-RE**

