 - ✧ Pain by visual analog scale (0-10) before, immediate and 5-min post exercise
 - ✧ Participant's acceptance by a Likert 5-point categorical scale after the whole program
- **Feasibility of BFR-RE**
 - ✧ Examination of drop-out rate and reasons of drop-out in those discontinuing the training
- **Unplanned readmission rate within 1 month of discharge for COPDAE**

Data analysis

SPSS version 17.0 will be used for statistical analysis.

The comparison of baseline characteristics of subjects across the 2 groups will be tested by independent t-test for continuous variables (e.g. age, anthropologic data, maximum voluntary isometric contraction of knee extension of dominant leg, hand grip strength of dominant hand, laboratory test results, spirometry data, 6-minute walk test, COPD Assessment test (CAT), etc.), Chi-square test for nominal variables (e.g. presence of myoglobin in urine, etc.).

For testing between-group and within-group changes after Blood flow restriction resistance exercise (BFR-RE), multivariate repeated measures ANOVA will be used.

All continuous variables are presented as mean \pm SD (standard deviation). The level of statistical significance was set at $p < 0.05$.

Sample size calculation

A priori power analysis (calculated by G*Power 3.1.9.5) showed that in order to have a power of 80% to detect a difference of medium effect (f^2 : 0.22) of muscle strength gain (Cook, 2017) at the 0.05 level of significance, 18 patients is needed in each group. If a dropout rate of 30% is estimated, 48 patients in total will be needed for the study.

Randomization

Participants are randomized into one of the two treatment groups. A computer compiles randomization list. Based on randomization, envelopes are made with participant number, including allocation of patients to BFR-RE vs. without BFR-RE. The envelopes are opened after inclusion for the individual participant only. The randomization list is kept in a sealed envelope.

Stratification of participants into two groups by maximum voluntary isometric contraction (MVIC) at baseline before randomization will be done. The cutoff for the stratification will be determined from the data in the recent service.

Blinding

Participants, doctors, nurses and involved Physiotherapists are for obvious reasons not blinded, but assessments at recruitment and on discharge will be carried out by blinded Physiotherapists without knowledge of treatment group.

Interruption

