The individual participant can withdraw from the study at any time. Participants

may also be excluded from the study at any time based on the investigator's evaluation.

Data registration

All data relevant for the study are recorded in a specific form.

Data of each enrolled participant are listed in a personal form.

Recruitment

Consecutive patients will be recruited in the three pulmonary wards in Haven of Hope Hospital between 10.6.2020 – 28.2.2021. The study will be expected to finish within 9 months or earlier if the expected recruitment achieved.

Expected Benefits

BFR-RE may improve the muscle strength of the knee extension and muscle size of quadriceps in the patients undergoing early rehabilitation for COPDAE. This may allow patients to actively participate the resistance training to improve the mobility function, subsequently health-related quality of life.

Adverse events

In this context, adverse events are defined as any unintended, unfavorable finding, symptom or disease that can be connected to the strength training, whether it is deemed to have a correlation with this or not. Adverse events are recorded by spontaneous registration as well as by open questioning.

Concerns on patient's safety

Delayed onset of muscle soreness (DOMS)

DOMS is normal after exercise, including after LL-BFR training. It was reported in 40% of participants in a survey before but this will subside within 24-72 hours (Patterson, 2018).

Numbness

Incidence of transient numbness is between <2% (Nakajima, 2006) to 18.5% (Patterson, 2018). This is related to the tourniquet pressure causing peripheral nerve compression.

Central vascular response

Continuous BFR-RE (keep restriction during rest period between sets) will

increase the heart rate (HR), systolic blood pressure (SBP), diastolic blood pressure (DBP), or double product (HR x SBP) compared with same exercise in free flow conditions.

Cardiac output is not affected by BFR during exercise since HR increases and stroke volume decreases proportionally compared to non-BFR groups. Changes in central hemodynamic response are blunted after BFR-RE when compared to HL-RE. However, there was reported to be 14.6% of fainting / dizziness related to BFR-RE (Patterson, 2018). The study is not blinded to the physical therapists; thus, the identification of any safety issues will be easy.

Venous thromboembolism (VTE)

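### The acceptance rating is timed for the end of the programme and none is stated for patients who stop early, so it could overstate acceptance if stopping is linked to dislike

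*Combined protocol and SAP*

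**What the plan says.** The introduction explains that BFR-RE is new to the hospital and that "acceptability and feasibility of this training will be explored as secondary outcomes". Under Secondary outcomes, acceptability has two measures. One is "Pain by visual analog scale (0-10) before, immediate and 5-min post exercise". The other is the Likert item, listed as "acceptance by a Likert 5-point categorical scale after the whole program".

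The section on determining acceptance of the programme words the timing a little differently: "5-point Likert scale will be given to participants after the additional muscle strength training". The Data collection timepoint section has two entries, baseline and "After completeness of training (i.e. at least 10 sessions of training". Completeness is defined there as 10 of 12 sessions.

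Early stopping is foreseen. The Interruption section says "The individual participant can withdraw from the study at any time", and the sample size section allows for 30% drop-out. For those who discontinue, the feasibility outcome records the drop-out rate and the reasons. The Data analysis section gives no denominator and no missing-data rule for the acceptance item.

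**The concern.** The reason given for measuring acceptability is that the technique is new to the hospital. For that purpose the views of patients who began the training and gave it up matter at least as much as the views of those who finished. If the form is handed out only once a patient has done 10 sessions or more, those who leave sooner drop out of both numerator and denominator.

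If some of them left because they disliked the training or found it very uncomfortable, the reported figure would look better than the experience of all who started. If they left for unrelated reasons such as transfer, illness or discharge, the completers' figure would be a fair guide to the rest. The plan as written cannot tell these situations apart on the acceptance scale itself, and a rating not taken when a patient stops is hard to recover afterwards.

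**Working it through.** **Reading the timing statements together.** The outcome list ties the item to the end of the whole programme. The only post-baseline timepoint requires at least 10 sessions. The definition of the scale ties it to the end of the additional training and speaks of participants, not completers. The first two point to completers; the third fits either reading. No section states a rating for a patient who stops before session 10.

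**Inputs from the plan.** The sample size section gives 18 needed per group, 30% drop-out and 48 in total. The total is reproduced by 18 × 1.3 = 23.4, rounded up to 24 per group, and 2 × 24 = 48. Equal allocation is assumed. The share of leavers, d, then follows in two ways:
- 24 - 18 = 6 leavers, so d = 6/24 = 25%.
- 30% of 24 = 7.2 leavers, so d = 30%.

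This allowance was made for the trial as a whole. It is not a stopping rate for the BFR arm. Treating it as the share unrated is an assumption.

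**Assumption not in the plan.** Acceptance (like or very like) among completers is p_c = 80%. Acceptance among leavers, p_d, is unknown and is varied.

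**Formula.** Acceptance among all starters = (1 - d) × p_c + d × p_d. The completers' figure therefore overstates it by d × (p_c - p_d).

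| Leavers' acceptance p_d | d = 25% | d = 30% |
|---|---|---|
| 100% | 0.25 × (0.8 - 1) = -5 points | 0.30 × (0.8 - 1) = -6 points |
| 80%, as completers | 0 | 0 |
| 0% | 0.25 × 0.8 = 20 points | 0.30 × 0.8 = 24 points |

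**In whole patients, worst case, against sampling error.** The half-width of the 95% Wilson interval is z/(1 + z²/n) × √[p(1 - p)/n + z²/(4n²)], with z = 1.96.
- 6 unrated: 14/18 = 78% among raters. If no leaver accepts, 14/24 = 58%, a drop of 19 points. The Wilson interval for 14/18 is 55% to 91%, half-width 18 points.
- 7 unrated: 14/17 = 82% among raters. If no leaver accepts, again 14/24 = 58%, a drop of 24 points. The Wilson interval for 14/17 is 59% to 94%, half-width 17 points.

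So the worst case is about one half-width with 6 unrated and clearly more than one with 7. The interval reflects sampling error among raters only; it makes no allowance for selective non-rating.

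**The case against.** The strongest reply is that the gap is inferred from silence. The definition of the scale can be read as a form given whenever a person's training ends, and nothing says early stoppers are left out. That reading is possible and is not ruled out here. It sits less easily with the whole-programme wording and the 10-session timepoint, and one sentence from the sponsor would settle it. The Blinding section says that "assessments at recruitment and on discharge will be carried out by blinded Physiotherapists", but it does not name the acceptance item among the discharge assessments.

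Second, leavers are partly covered. Pain is scored around exercise, not at programme end. Drop-out reasons are recorded. "Adverse events are recorded by spontaneous registration as well as by open questioning", according to the Adverse events section. Dislike that led to stopping could therefore appear beside the Likert result. This stands as mitigation, but none of these is an acceptance rating and none enters the Likert figure.

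Third, whole-programme acceptance is a legitimate question, and a patient who attended one session cannot answer it. That is right. It argues for showing early ratings separately, not for leaving them uncollected.

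Fourth, the 30% is an allowance for the strength analysis, and no rate of stopping from dislike is given. That also stands, and it is why the figures above are illustrations only.

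A reader might go further and infer that early stoppers are deliberately excluded, or that acceptance will be overstated. The documents support neither: exclusion is not stated, and the direction of any bias depends on leavers' unknown views. The instruction to stop training for dizziness or severe discomfort does not supply the missing link, because it can be read as ending that session only.

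**Conclusion.** The concern holds in a limited, conditional form. On the more natural reading of the timing, the acceptance result will describe mainly patients who completed at least 10 sessions, and no rating is stated for the rest. It could overstate acceptance among starters if stopping is linked to dislike; it does not if stopping is unrelated.

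The illustrative range, about -6 to +24 points, rests on 24 per arm, 80% acceptance among completers and 25% to 30% unrated. Only the arm size and the drop-out allowance trace to the plan. The figures concern acceptance within an arm. The documents do not fix the direction of any effect on a comparison between arms, which would depend on who stops in each.

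The point is worth considering because the remedy is cheap. It should not be ranked higher: the item is exploratory, no decision rule rests on it, and the primary MVIC result is unaffected by how it is collected.

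**What to change.** Give the same Likert item to every participant who started at least one session, at the last session attended or when training stops, and record the number of sessions attended. Report by arm the number rated out of the number started. Show completers (at least 10 sessions) and early stoppers separately as well as together, beside the drop-out reasons, so that ratings after partial exposure stay distinguishable from whole-programme ratings.

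If early ratings cannot be obtained, report at least the number rated out of the number started. If the sponsor already intends to rate early stoppers, a sentence saying so, plus that denominator, would be enough.

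The cost is earlier timing of a one-item form and a few table rows. The downsides are some missed or refused forms (for example after withdrawal or urgent transfer), early ratings based on partial exposure, and a possibly less favourable figure.

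### The planned two-timepoint ANOVA is valid, but an ANCOVA on baseline MVIC would usually estimate the arm difference more precisely at negligible cost

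*Combined protocol and SAP*

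**What the plan says.** The primary outcome is a single continuous measure: "Maximal voluntary isometric contraction (MVIC) of knee extension of the dominant leg, with a unit Newton (N), will be assessed by computer dynamometry". Under "Data collection timepoint" the protocol lists two occasions, baseline and "After completeness of training (i.e. at least 10 sessions of training".

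The only method named for change is in the Data analysis section: "For testing between-group and within-group changes after Blood flow restriction resistance exercise (BFR-RE), multivariate repeated measures ANOVA will be used". That section names no covariate, no adjustment for baseline and no primary contrast. In it, baseline MVIC appears only in the t-tests that compare baseline characteristics between arms.

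The Randomization section does treat baseline MVIC as important: "Stratification of participants into two groups by maximum voluntary isometric contraction (MVIC) at baseline before randomization will be done", and "The cutoff for the stratification will be determined from the data in the recent service". It describes no blocking within strata.

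The sample size is set to "detect a difference of medium effect (f^2 : 0.22) of muscle strength gain", with 18 patients per group for 80% power at the 0.05 level. It then adds: "If a dropout rate of 30% is estimated, 48 patients in total will be needed for the study".

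**The concern.** With two arms and two occasions, a repeated measures ANOVA treats baseline MVIC as the first of two responses. Its group-by-time test compares mean change between arms, so one newton at baseline is taken to predict exactly one newton after training. ANCOVA estimates that slope from the data. Both analyses need the same two measurements per patient, so the switch costs no patients and no new data.

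Precision matters here because the trial is small. With 30% dropout, 48 recruited patients leave 48 x 0.7 = 33.6, or about 34, against the 36 the calculation calls for.

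A lesser point is that the plan does not say which ANOVA effect answers the between-arm question. The sample size text speaks of strength gain, which points to group-by-time. The group main effect averages baseline and post-training values and would be a much weaker test.

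**Working it through.** **Inputs from the documents:** f^2 = 0.22 on strength gain, alpha 0.05, 80% power, 18 per group, 48 recruited, 30% dropout.

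**Assumptions:** two-sided test; MVIC analysed alone; f^2 read literally and held fixed on the change score; rho from 0.5 to 0.95; k = post-training SD / baseline SD, set at 0.9, 1.0 and 1.2.

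**1. The plan's own figure.** For two groups d = 2 x sqrt(0.22) = 0.938. The normal approximation gives 2 x (1.960 + 0.842)^2 / 0.88 = 17.8, so 18 per group, as stated. The exact test gives 78.1% power at 36 patients and reaches 80% at 38.

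**2. Identity.** On a simulated two-group, two-occasion data set of 36 patients, the group-by-time F was 3.6927 and the squared t on change was 3.6927, with 34 error df. They are the same test.

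**3. Variances, in units of the baseline variance.**
- Change score: 1 + k^2 - 2k·rho.
- ANCOVA residual: k^2(1 - rho^2).
- Difference: (1 - k·rho)^2, where k·rho is the true baseline slope. It is never negative, and is zero only when the slope is 1.
- With k = 1 the ratio of ANCOVA to change-score variance is (1 + rho)/2.
- Estimating the slope costs one df and, for chance baseline imbalance, a factor 1 + 1/(34 - 4) = 1.033.

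**4. Power at 34 evaluable (noncentral F).** Planned test: lambda = 0.22 x 34 = 7.48 on 1 and 32 df, power 75.6%. ANCOVA: lambda = 7.48 x (variance ratio, change to ANCOVA) / 1.033 on 1 and 31 df. For example, at k = 1 and rho = 0.5, lambda = 7.48 / 0.75 / 1.033 = 9.65 and power is 85.3%.

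| ANCOVA power (%) | rho 0.5 | 0.7 | 0.8 | 0.9 | 0.95 |
|---|---|---|---|---|---|
| k = 0.9 | 89.1 | 85.3 | 83.5 | 82.5 | 83.5 |
| k = 1.0 | 85.3 | 80.7 | 78.4 | 76.2 | 75.2 |
| k = 1.2 | 79.7 | 75.5 | 74.2 | 75.1 | 79.5 |

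With k = 1 the 95% CI is narrower by about 12%, 6%, 3%, 1% and 0%.

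**5. Largest loss.** At slope 1 only the penalty remains: lambda = 7.48 / 1.033 = 7.24, power 74.1%, a loss of 1.5 points. The case k = 1.1 with rho = 0.9 (slope 0.99) gives the same 74.1%.

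**6. Effect of stratification (simulation, 20,000 trials per setting, equal SDs).** If arms are balanced within a median split of baseline MVIC, the unadjusted change test rejects a true null 3.5% of the time at rho 0.5 and 4.6% at 0.95, so it is conservative. Power in that setting is 76.8% against 86.0% for ANCOVA at rho 0.5, and 76.0% against 81.0% at 0.7. With unblocked allocation the null rejection rate is 4.9% to 5.1% for rho 0.5 to 0.9.

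**7. Other reading of the effect size.** If 0.22 is f in a 2 x 2 repeated measures design, 36 patients follow at rho = 0.6. Holding that raw effect (0.88 SD) fixed at 34 patients with equal SDs, planned against ANCOVA power is 70.1/80.6%, 79.4/86.3%, 89.5/92.8% and 97.6/98.3% at rho 0.5, 0.6, 0.7 and 0.8.

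**8. Group main effect.** Read as the between-arm test, it would have 33%, 20%, 14%, 9% and 7% power at rho 0.5, 0.7, 0.8, 0.9 and 0.95 (34 patients, equal SDs).

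**The case against.** The strongest reply is that nothing is broken. Under randomisation the change-score test is valid and unbiased, and no conclusion drawn from it would be unsound. The size of any gain rests on two quantities the documents omit. With equal SDs it is 3 points or less once rho reaches 0.8, and with a post-training SD 20% larger it is +4, 0 and -1.4 points at rho 0.5, 0.7 and 0.8. All of this stands, and it makes the point an improvement rather than a correction.

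Two further objections stand as conditions. If *multivariate* means several outcomes tested jointly, the interaction test is no longer a t-test on MVIC change; the single-outcome reading is reasonable but remains an assumption. The plan also promises within-group changes, which an ANCOVA does not test, so the replacement text must say what becomes of them.

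Against this, the risk is lopsided. The loss cannot exceed about 1.5 points under these assumptions, while the gain is about 10 points at rho 0.5 with equal SDs and 7 to 13 points across the whole rho range if the post-training SD is 10% smaller.

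**Conclusion.** The point holds as a precision improvement at negligible cost. It assumes that MVIC is analysed as a single outcome and that group-by-time is the between-arm test. At 34 evaluable patients the planned test has 75.6% power on the literal f^2. ANCOVA ranges from about 74% to 89% over the settings examined and is usually the higher of the two.

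Some stronger statements are tempting, but the documents do not support them:

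- A reader might infer that the planned test is invalid. It is not. Nor can it be called conservative on the present text, because conservatism requires balance within strata and no blocking is described.
- A reader might infer a fixed gain of about 10 points, a gain that vanishes at very high rho, or that ANCOVA reaches 80% only when rho is below about 0.73. These are equal-SD results. At k = 0.9 ANCOVA exceeds 80% at every rho examined; at k = 1.2 it is 79.7% even at rho 0.5.
- A reader might infer that ANCOVA makes up for having 34 rather than 36 evaluable patients. It may or may not, depending on unknown quantities, and the dropout allowance is a separate matter.

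**What to change.** In the Data analysis section, state that the primary between-arm analysis is an ANCOVA of post-training MVIC on arm, with baseline MVIC as a continuous covariate, reporting the adjusted difference in newtons with its 95% CI. Report within-group changes as descriptive summaries.

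Use the same form, each with its own baseline, for the continuous secondary outcomes (6-minute walk, grip strength, CAT, and SPPB if its total score is treated as continuous). No power was computed for these.

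A separate stratum term is not needed, because continuous baseline MVIC carries most of the same information. In the balanced simulation, adding it lowered ANCOVA power by about 1 point.

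If the ANOVA is kept, name group-by-time on MVIC alone as the primary test.

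The cost is two or three sentences, no new data, one degree of freedom and at most about 1.5 power points.

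### The planned 48 patients do not keep the 18 per group that the plan says it needs after 30% dropout, and the label 'medium' covers a detectable difference of nearly 1 SD of the strength gain

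*Combined protocol and SAP*

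**What the plan says.** The Sample size calculation section describes an a priori G*Power analysis for "a power of 80% to detect a difference of medium effect (f^2 : 0.22) of muscle strength gain". It continues: "at the 0.05 level of significance, 18 patients is needed in each group". It then allows for attrition: "If a dropout rate of 30% is estimated, 48 patients in total will be needed for the study".

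Three other parts of the combined protocol and SAP bear on this:

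- **Primary outcome.** This is the maximal voluntary isometric contraction (MVIC) of knee extension in the dominant leg, "with a unit Newton (N), will be assessed by computer dynamometry".
- **Data collection timepoint.** There are two occasions: baseline, and "After completeness of training (i.e. at least 10 sessions of training").
- **Data analysis.** For changes between and within groups, "multivariate repeated measures ANOVA will be used". Results are summarised as mean and SD and judged at p < 0.05. No confidence interval is mentioned.

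The documents do not give the G*Power procedure, the number of measurements entered, the correlation between measurements, the sidedness of the test, an SD for MVIC, or a target difference in Newtons.

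**The concern.** There are two linked problems.

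First, the total of 48 is presented as covering 30% dropout from a requirement of 36 evaluable patients. Taking 30% from 48 does not leave 36. On the plan's own figures, the trial is expected to finish below the size that it says it needs.

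Second, a reader may take the power sentence to mean that the trial is well placed to detect a moderate benefit of the device. Converted to the scale of the planned comparison, the printed effect is close to one SD of the gain. If that is not visible, a non-significant primary result could be read as evidence against a moderate benefit, which a trial of this size cannot give.

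**Working it through.** **Inputs from the documents:** 18 per group, 48 enrolled, 30% dropout, 80% power, significance level 0.05, effect printed as f² = 0.22, two measurements.

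**Assumed:** a two-sided test, equal groups, and (where needed) a correlation between the two measurements.

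**1. The plan's 18 per group**

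For two groups, d = 2f = 2 × √0.22 = 0.938, so d² = 0.88.

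- Normal approximation: n = 2 × (1.960 + 0.842)² / 0.88 = 15.70 / 0.88 = 17.84, rounded up to 18. Power at 18 is 80.4%.
- Exact non-central F, with λ = f² × N and 1 and N − 2 degrees of freedom: at N = 36, λ = 7.92 and power is 78.1%. At N = 38, λ = 8.36 and power is 80.3%, so the exact requirement is 19 per group.

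The plan's figure is therefore reproduced to within one patient per group and two points of power.

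**2. Dropout**

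- 18 × 1.3 = 23.4, rounded up to 24 per group, gives 48. This matches the plan and suggests that 30% was added.
- Dividing it out gives 18 / 0.7 = 25.7, rounded up to 26 per group, or 52 in total (52 × 0.7 = 36.4).
- 48 × 0.7 = 33.6, about 34 evaluable or 17 per group. A total of 48 keeps 36 only if dropout is 12/48 = 25%.

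**3. What 18 and 17 per group can detect**

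With two measurements, the group-by-time F test is the two-sample test on the gain. Exact results, with differences in SD of the gain:

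| | 18 per group | 17 per group |
|---|---|---|
| Power at 0.94 SD (f² = 0.22) | 78% | 76% |
| Power at 0.775 SD (f² = 0.15) | 62% | 59% |
| Power at 0.5 SD | 31% | 29% |
| Difference giving 80% power | 0.96 SD | 0.99 SD |
| 95% CI half-width, t × √(2/n) | 0.68 SD | 0.70 SD |

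If 33 patients remain (16 and 17), 80% power needs 1.01 SD.

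**4. If 0.22 was entered as f in a group-by-time interaction**

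Here λ = f² × N × m / (1 − ρ), with m measurements and correlation ρ. For m = 2 the difference in SD of the gain is 4f / √(2(1 − ρ)) = 0.88 / √(2(1 − ρ)).

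- ρ = 0.5: λ = 0.0484 × 36 × 2 / 0.5 = 6.97. Power is 73% at 36 patients and 70% at 34; 80% needs 44. The difference is 0.88 SD of the gain.
- ρ = 0.6: λ = 8.71. Power is 82% at 36 and 79% at 34. The difference is 0.98 SD.
- 80% is reached at ρ = 0.58 with 36 patients (0.96 SD) and at ρ = 0.61 with 34 patients (0.99 SD).

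The detectable difference on the gain scale is the same as in step 3.

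**5. The label**

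The usual conventional marks, which are not in the documents, are 0.8 for a large d and 0.40 for a large f. The printed effect exceeds both (0.938 and 0.469). On the regression f² scale it lies between medium (0.15) and large (0.35).

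**The case against.** The strongest reply is that the stated power is nearly right. On the printed effect, 18 per group gives 78% exactly and 80.4% by the normal approximation. A difference of one patient per group is not a material error. This stands. A reader might infer that the 18 per group is a miscalculation, and the documents do not support that.

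A reader might also infer that 0.22 was really f and that true power is 73%. That figure depends on an assumed correlation of 0.5; at 0.6 the power is 82%. The documents give no correlation. Three measurements at a correlation of 0.5 would also yield 36 patients (81.5% power), but the plan has two measurements and nothing shows that three were entered. Neither reconstruction can be asserted.

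Nor is 'medium' wrong on every scale. It is arguable on the regression f² scale, and roughly right if f was meant, where the usual mark is 0.25. The objection is to using the word without a scale.

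The plan makes no claim about 0.5 SD, so the 31% is an illustration and not a contradiction of the text. Finally, the dropout slip costs little: about two points of power and 0.03 SD.

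None of this removes the two points that remain. The step from 48 to 33.6 uses only the plan's own numbers, and the 0.96 and 0.99 SD limits do not depend on which input was used.

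**Conclusion.** The point holds in a limited form. With 30% dropout, 48 enrolled leaves about 34 evaluable patients, not the 36 that the plan requires; 52 would be needed to keep 36. Exact power for the printed effect is then about 76%, against a stated 80%. The difference detectable with 80% power is about 0.99 SD of the gain, or 0.96 SD if 18 per group were kept. The word 'medium' does not convey this.

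The dropout result needs no assumption beyond equal groups and a dropout rate expressed as a share of those enrolled. The power figures assume a two-sided 0.05 test of the difference in gain, which is what the planned analysis amounts to with two measurements. The 76% also takes f² = 0.22 as printed.

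The missing G*Power inputs and the missing difference in Newtons are gaps in detail. They prevent the calculation from being checked in full, but they do not show that it is wrong.

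**What to change.** Replace the power and dropout sentences in the Sample size calculation section with wording such as:

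> *48 enrolled with 30% dropout leaves about 34 evaluable patients. This gives about 76% power (two-sided 0.05) for a between-group difference in MVIC gain of 0.94 SD of the gain (f² = 0.22), and 80% power for about 0.99 SD.*

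This difference in SD of the gain should stand in place of the unqualified 'medium'. If f was the value entered, correct f² to f, state the number of measurements and the correlation used, and adjust the 76% clause to match; the 0.99 SD clause is unaffected.

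In the Data analysis section, add the 95% confidence interval for the between-group difference in MVIC gain. At 17 per group its half-width is about 0.70 SD of the gain. Even an observed difference of zero would leave 0.5 SD inside the interval, and a null result should not be read as excluding a moderate benefit.

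The cost is wording, retrieval of the G*Power inputs and one added interval. No further patients, visits or measurements are needed. The downside is that the stated power and detectable effect become slightly less favourable.
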